- Subjects with suicidal ideation where outpatient BA treatment is determined unsafe or inappropriate by the study clinician. These patients will be immediately referred to appropriate clinical treatment.
- History or current diagnosis of any of the following DSM-5 psychiatric illnesses: schizophrenia spectrum or other psychotic disorder, bipolar disorder, OCD, substance (including alcohol) use disorder within the past 12 months or lifetime severe substance use disorder (i.e., meeting former DSM-IV criteria for past substance dependence). Simple phobia, social anxiety disorder, panic disorder, generalized anxiety disorder, and PTSD will be allowed (unless study clinician determines PTSD is primary diagnosis and requires treatment prior to depression/anhedonia treatment).
- Meet criteria for chronic depression (current episode > 2 years)
- Currently receiving psychotropic treatment or psychotherapy
- Current use of psychotropic medication with the exception of SSRIs (See section on Concomitant Medications (see p. 4))

B. Healthy Control Adolescents: Anticipated enrollment = 65 (age-matched to serve as healthy controls).

Additional Exclusion Criteria:

- Elevated depressive symptoms as assessed in phone screen
- History of meeting criteria for any DSM-5 psychiatric or substance-related disorder
- Current use of any psychiatric medications
- First degree relative diagnosed with MDD, Bipolar Disorder or Psychotic Disorder

Adult Cohort

C. Parent: Anticipated enrollment = 70

Inclusion Criteria:

- English as first language or English fluency

Concomitant Medications:

Anhedonic adolescents being treated with any SSRI (e.g., fluoxetine (Prozac), fluvoxamine (Luvox), sertraline (Zoloft), paroxetine (Paxil), citalopram (Celexa), and escitalopram (Lexapro)) may participate in the active treatment as long as they have not made a change in medication for at least 4 weeks prior to enrollment. Those who are being treated with any other psychiatric medications will be excluded. In order to limit attrition and to mirror real world clinical practice, participants will be permitted to make BWH/MGH Human Subjects Research Application Form

Version 4: March 2002

PARTNERS HUMAN RESEARCH COMMITTEE DETAILED PROTOCOL

changes in the dose of their SSRI during the course of the treatment. If a participant's clinical status worsens to the degree that a new medication is necessary, the participant will have the opportunity to complete the BA course and scheduled assessments.

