Analyses will be conducted to determine if there are statistical differences in symptom, behavioral, and/or neural measurements between participants on SSRIs versus participants on SSRIs plus other psychiatric medications.

Of note, participants' outpatient psychiatrists will prescribe all medications and study personnel will play no role in medication decision-making. Moreover, participants will not go through any medication washout as part of this study. Participants who are interested in coming off a medication to enter the study will be instructed to discuss this with their outpatient psychiatrist. Each participant's current medication and dosage will be tracked via communication with the participant's parents, unless the participant is an adult (18 years old) in which case we will communicate with them directly. This practice is consistent with protocol 2012P001844, a study which also focuses on psychotherapy for depressed adolescents.

Recruitment

Subjects will be recruited through the following methods:

- *Fliers.* Fliers will be hung on the McLean campus as well as throughout the greater Boston area (i.e., within a 25-mile radius of the hospital).
- *Internet advertisements.* Advertisements will be posted on websites (e.g., Craigslist, Facebook, Nextdoor, Rally)
- *Direct mail.*
 - Through a Partners-approved vendor, we will mail postcards advertising our study to families with adolescents between 13 and 18 years of age. The ad will include IRB-approved language adapted from approved study fliers. Furthermore, our lab will not receive any demographic information about the families who will receive the advertisements, as all of the mailing will be done through the approved vendor. Additionally, the ads will include the following note: "Note: You are receiving this postcard as part of a commercial mailing list of families with adolescents between 13-18 in the greater Boston area."
 - Sending a letter to "RODY Yes" patients within Research Patient Data Registry (RPDR)
- *Schools.* When invited by school administrators, the PI will make presentations in schools to school administrators, teachers, and parents. Additionally, the study staff will provide study flyers to schools that wish to hang them in guidance counselor offices. These presentations and flyers will be available to schools within a 25-mile radius of McLean.

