The adolescent portion of the study includes the following cohorts: (a) 35 anhedonic adolescents receiving BA and (b) 35 healthy control adolescents. The primary aim is to examine whether anhedonic and healthy adolescents differ on baseline neural (fMRI), behavioral (PRT) and self-report (EMA) measures of reward function, as well as whether behavioral and neural mechanisms prospectively predict and mediate symptom improvement among anhedonic adolescents receiving BA. Importantly, within the active treatment cohort, analyses will be conducted to determine if there are statistical differences in symptom, behavioral, and/or neural measurements between medicated and non-medicated depressed adolescents. Additional analyses will examine if there are statistical differences between participants on SSRIs versus participants on SSRIs plus other psychiatric medications.

Descriptive and Exploratory Analyses:

Descriptive statistics and exploratory graphical techniques, such as frequencies, means, medians, histograms, and box plots will be used to assess skewness and/or outliers in the data. Continuous/quantitative variables will be appropriately transformed when necessary, e.g., via log transformation for positively skewed distributions. For outcomes acquired during treatment, the analytical approach will address the type of outcome, as well as accommodating the within-individual correlation due to repeated assessments. In

PARTNERS HUMAN RESEARCH COMMITTEE DETAILED PROTOCOL

addition, the results will be assessed for sensitivity to dropouts or missing data. The primary analysis will be an intent-to-treat analysis, which includes all subjects. Of note, attempts will be made to continue assessing subjects even if they drop out of treatment.

Behavioral Variables:

For the PRT, the primary variable of interest will be *Reward Learning*, operationalized as the increase in response bias (RB) scores from Block 1 to Block 3 [$\Delta RB = RB(\text{Block 3}) - RB(\text{Block 1})$]. This variable was selected because it has been repeatedly linked to current and future anhedonic symptoms (Pizzagalli et al. 2005; 2008).

EMA-Derived Variables:

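### Does the planned comparison of SSRI users with users of SSRIs plus other psychiatric medications need to be redefined or dropped?

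*Combined protocol and SAP*

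**What the plan says.** Two entry rules in section III fix who can be in the groups at baseline. The additional exclusion criteria for the anhedonic cohort list "Current use of psychotropic medication with the exception of SSRIs", and the Concomitant Medications text says of other drugs: "Those who are being treated with any other psychiatric medications will be excluded". Another exclusion in the same list reads "Currently receiving psychotropic treatment or psychotherapy".

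Other rules deal with what happens later. Under Concomitant Medications, a participant whose "clinical status worsens to the degree that a new medication is necessary" may still complete BA and the scheduled assessments. Section VII, items (f) and (i), also keeps in the study a participant who starts an excluded medication, without naming a reason for the prescription.

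The comparison is planned twice. In section III, directly after the new-medication rule, symptom, behavioral and neural measurements are to be compared "between participants on SSRIs versus participants on SSRIs plus other psychiatric medications". In section VI, under Sample Size, it follows a comparison of "neural measurements between medicated and non-medicated depressed adolescents" within the treated cohort and is introduced as additional: "Additional analyses will examine if there are statistical differences between participants on SSRIs versus participants on SSRIs plus other psychiatric medications".

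Section III also says that each participant's "current medication and dosage will be tracked via communication with the participant's parents" (or directly with participants aged 18). Section VII (i) has the BA therapist record changes throughout the study.

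**The concern.** Set beside the entry rules, the comparison seems to name a group that cannot exist. Nobody may enter on an SSRI plus another psychiatric drug, so at pre-treatment one side of the contrast has no members.

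The group can form only after enrolment, and three difficulties then appear:

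- The plan does not say at which assessment groups are formed, or whether exposure means ever or current use, or a start before the outcome is measured. These choices could be made after the data are seen.
- The group could be too small for any test.
- The only reason section III gives for a new drug is clinical worsening. To the extent that starts follow worsening, a later symptom difference partly reflects the course that led to the prescription and cannot be read as an effect of the drug.

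The exclusion for current psychotropic treatment, read alone, would also empty the SSRI-only group at entry. At stake would be a secondary result that is either impossible to produce or easy to misread.

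**Working it through.** **Is there a figure to reproduce?** No. The plan gives no alpha, power, effect size or SD for this comparison. The only sizes are 35 anhedonic adolescents (section VI, Sample Size) and an anticipated enrollment of 65 (section III).

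**Group membership from the text.** At entry, SSRIs are the only psychotropic medication allowed, so the SSRI-plus-other group has 0 members at pre-treatment. After entry, sections III and VII (f) and (i) keep participants who start another drug. The group is therefore defined by post-enrolment starts. This needs no assumption.

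**Group size.** The documents give neither the share on SSRIs (s) nor the share of those adding a drug (a). Assumed low, middle and high pairs (s, a) are (20%, 5%), (40%, 12.5%) and (60%, 20%). The number of members is k ~ Binomial(N, p) with p = s × a, so the expected number is N × p and P(k ≤ 1) = (1 − p)^N + N p (1 − p)^(N−1).

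Middle case, N = 35: p = 0.4 × 0.125 = 0.05; expected 35 × 0.05 = 1.75; P(k ≤ 1) = 0.166 + 0.306 = 0.472.

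Overall power is for a true difference of 0.8 SD: two-sided 5% t test, noncentral t, averaged over the possible group sizes, with k of 0 or 1 counted as no test.

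| N | Case | Expected k | P(k ≤ 1) | P(k ≥ 3) | Overall power, 0.8 SD |
|---|---|---|---|---|---|
| 35 | low | 0.35 | 95% | 0.5% | 0.6% |
| 35 | middle | 1.75 | 47% | 25% | 10% |
| 35 | high | 4.2 | 7% | 81% | 27% |
| 65 | low | 0.65 | 86% | 3% | 2% |
| 65 | middle | 3.25 | 16% | 64% | 23% |
| 65 | high | 7.8 | 0.2% | 99% | 48% |

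**Detectable difference at 80% power** (same test): 3.2 SD for 1 against 13, 2.3 SD for 2 against 12, 1.8 SD for 3 against 18, 1.6 SD for 4 against 17. By the normal approximation, 80% power at 0.8 SD needs 2 × (1.96 + 0.84)² / 0.8² = 24.5, so 25 per group. The test is weak in every case, but whether it can be run at all depends on rates that nobody has stated.

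**How far worsening could mislead.** In an illustration with N = 35, middle rates and no drug effect on symptoms, starters who follow worsening are those highest on a propensity correlated 0.3, 0.5 or 0.7 with symptom worsening. At least two starters occur, so the test can be run, in about 53% of trials.

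| Starts that follow worsening | Significant when run (0.3 / 0.5 / 0.7) | Significant over all trials |
|---|---|---|
| all | 10 / 21 / 41% | 5.5 / 10.7 / 21.4% |
| half | 7 / 10 / 16% | 3.5 / 5.2 / 8.4% |
| none | 5% | 2.7% |

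A significant result here shows a true difference in course between the groups. It would be wrong only if it were reported as a drug effect.

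**What the plan claims.** Both places promise a search for differences. Neither attributes a difference to medication, and Specific Aims 1 to 3 do not use the comparison. The primary analysis is intent-to-treat in all subjects, so it does not depend on how these groups are formed.

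**The case for a change.** The strongest case for a change is that it would be cheap. A sentence in sections III and VI could fix the time point and exposure rule, or turn the test into a listing of participants who start a drug, mostly from records the plan already keeps. The Sample Size text marks the medication comparisons as important, so they are likely to be reported. Without a rule, the grouping could be chosen after the results are known. Little power would be lost: even with 65 enrolled and both rates high, it is 48% for 0.8 SD and 65% for 1.0 SD.

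Much of this stands. The baseline emptiness and the missing exposure rule are facts of the text, and the power is poor throughout the assumed range.

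The need for a change does not follow. Section III puts the comparison directly after the new-medication rule, so participants who add a drug during the study are the natural reading. A listing of SHAPS scores alone would give up the behavioral and neural comparisons, although the argument about worsening was made for symptoms and no size was shown for PRT or fMRI. Fixing the medicated versus non-medicated contrast at pre-treatment would only write down a definition; no fault in that contrast was shown beyond the missing time point.

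The exclusion for current psychotropic treatment does conflict with the SSRI allowance if read literally, and the sponsor must reconcile the two wordings. It is a separate matter of eligibility wording. The adjacent exclusion, the Concomitant Medications text and section VII (f) all provide for SSRI use, so the conflict does not make this analysis unworkable.

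**Conclusion.** No change to the analysis plan is needed. The second group is empty at pre-treatment and forms only after enrolment, and the plan leaves its timing and exposure rule unstated. That is missing detail in an additional analysis, and analysts can fill it sensibly: form the group from the tracked medication record, report how many are in it, and describe rather than test a group of one or two. A later symptom difference should not be called a medication effect, and the plan does not call it one.

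The empty baseline group rests on the text alone. The expected sizes (0.35 to 4.2 of 35; 0.65 to 7.8 of 65) and the power (0.6% to 48% for 0.8 SD) rest wholly on assumed SSRI and add-on rates. The false-positive illustration also rests on assumed correlations and an assumed share of starts that follow worsening. Under none of these assumptions does an aim or the intent-to-treat analysis change.

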Anhedonic adolescents will undergo a 12-week protocol of BA treatment. Neural (fMRI) and behavioral (PRT) measures will be assessed at pre- and post-treatment, and the EMA protocol will involve repeated assessment waves. We hypothesize that:

PARTNERS HUMAN RESEARCH COMMITTEE DETAILED PROTOCOL

- (a) Pre-treatment reward dysfunction (i.e., assessed via baseline fMRI, PRT and EMA), controlling for overall pre-treatment levels of depressive symptoms, will predict anhedonic (Snaith–Hamilton Pleasure Scale [SHAPS; Snaith et al., 1995]) symptom improvement over the course of BA.
- (b) Greater pre- to post-treatment normalization in neural (i.e., striatal and mPFC response to fMRI task) and behavioral (i.e., PRT performance) measures will be linked to greater anhedonic symptom improvement over the course of treatment.
- (c) Given emerging evidence of decreased cortico-striatal functional connectivity to reward-related stimuli in depression (Admon et al., 2015), we expect that BA will result in significant increases in cortico-striatal functional connectivity to rewarding stimuli from pre- to post-treatment.

(3) **Specific Aim 3:** Examine association between changes in neural reward circuitry and real-world positive affect and anhedonia: The EMA protocol will be implemented to acquire a more fine-grained and “real-world” assessment of changes in subjective positive affect (PA) and anhedonia, as well as the acquisition and use of BA skills, over the course of treatment. We hypothesize that:

- (a) Following BA, participants will report improvements in daily PA and anhedonia and increased use of BA skills.
- (b) Integrating across units of analyses (i.e., neural, behavioral and self-report), we expect that greater pre- to post-treatment normalization of striatal and mPFC response, cortico-striatal connectivity, as well as PRT performance will be associated with greater improvements in daily reports of PA and reduced anhedonia, as well as use of BA skills.

III. SUBJECT SELECTION

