Due to revised COVID-19 procedures, participants may elect to complete their screening session remotely. With the participant's verbal consent, the research assistant will email a copy of the Consent/assent form(s) prior to the remote session. The research assistant and participant will discuss all study procedures via telephone or a Partners-issued Zoom account (<http://pcm.partners.org/services/movi.aspx>). The participant will be reminded they can withdraw at any time. REDCap eConsent will be used to obtain signatures and a signed copy will be distributed to the participant electronically according to ERIS guidance (<https://confluence.partners.org/display/shareit/27233366/HOX07266265b398484fada0c1b491a15c5aYOP>)

V. STUDY PROCEDURES

A. Parent Initial Assessment – Day 1 (Approximately 1 hour)

Semi-Structured Clinical Interview

(1) Miniature International Neuropsychiatric Interview (MINI; Sheehan et al., 1998) The MINI is a structured interview assessing for Axis I psychopathology symptoms (e.g., mood, anxiety, substance abuse, psychosis). Each MINI diagnostic module consists of a series of screening items followed by questions about specific symptomatology.

Self-Report Measures

- (1) Beck Depression Inventory-II (BDI-II; Beck et al., 1996). The BDI-II is a 21-question self-report inventory for measuring the severity of depression.
- (2) Snaith-Hamilton Pleasure Scale (SHAPS, Snaith et al., 1995). This 14-item self-report questionnaire asks participants to rate their ability to experience pleasure when doing various activities. This instrument assesses hedonic capacity.
- (3) Temporal Enjoyment of Pleasure Scale (TEPS; Gard et al., 2006). The TEPS is an 18-item self-report measure assessing anticipatory and consummatory aspects of pleasure
- (4) Positive and Negative Affect Schedule – Trait Version (PANAS; Watson et al., 1988). The PANAS is a 20-item self-report measure that assesses positive and negative affect symptoms.
- (5) Perceived Stress Scale (PSS; Cohen et al., 1983). The PSS is a 10-item self-report questionnaire assessing the extent to which the participant perceives stress in his/her life.
- (6) Contact Information & Demographic Forms (Relating to Parent & Child)

Parent-Report of Adolescent Mood and Symptoms

**PARTNERS HUMAN RESEARCH COMMITTEE
DETAILED PROTOCOL**

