(2) *Self-Referent Encoding Task (SRET; Gotlib et al., 2004)*. The SRET is an information processing task that has participants encode and recall adjectives while fMRI data is being obtained. We will use 22 depressotypic, 22 socially threatening, and 22 physically threatening words. To balance the number of negative and positive words, we used 50 positive words. Examples of the words include “loving” for the positive category, “sad” for the sad emotion category, “teased” for the social threat category, and “choking” for the physical threat category. All words will be presented on a computer monitor, and at the conclusion of the task, subjects will be asked to recall adjectives presented on the screen. The task takes approximately 10 minutes.

Following the fMRI session we will re-administer the PANAS-State Version.

Sustained Attention to Response Task (SART; Van Schie et al., 2012). In the sustained attention to response task (SART; Van Schie et al., 2012), participants are instructed to press the spacebar as fast and accurately possible when frequent non-targets (numbers 0-2; 4-9) are presented on a computer screen, and to withhold response to an infrequent target (number ‘3’). Performance is assessed with RT and errors. A total of 72 targets (on 1040 trials) are randomly presented within four blocks of 5 mins each. In addition, 4 probe questions appear (after each block) to inquire about mind-wandering: Participants indicate if just prior to the probe, they were a) on-task, b) off-task because of an external distraction (e.g., noise), or c) had a task-unrelated thought. The frequency (%) of each category is calculated.

PARTNERS HUMAN RESEARCH COMMITTEE DETAILED PROTOCOL

This SART task will allow us to collect important preliminary data on the relationship between sustained attention and depressive symptoms (including anhedonia). In addition, the K23 study includes EMA measures of rumination and mind-wandering. We wish to test the relation between ecologically valid (EMA) measures of rumination/mind-wandering (both linked to depression) and sustained attention on a computerized performance task.

D. Parent Behavioral Task and Self-Report (Approximately 1 hour)

While the child is completing their questionnaire and the behavioral task (PRT). The Parent will complete the BDI-II, SHAPS, PANAS and MFQ-PR. In addition, they will complete the PRT.

E. Behavioral Activation (BA) Treatment with Anhedonic Adolescents:

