
Participants will be contacted at regular intervals to ensure high EMA completion.

PARTNERS HUMAN RESEARCH COMMITTEE DETAILED PROTOCOL

F. Post-Treatment Adolescent Assessment (Approximately 3 hours):

Within 10 days of the final BA session, anhedonic participants will return for a post-treatment assessment lasting approximately 3 hours. Healthy control participants will also complete the same assessment 12-13 weeks after their initial assessment. Adolescents will be asked to complete self-report measures assessing symptoms/affect (MFQ, CES-D, SHAPS, TEPS, MASC, PANAS), stress (PSS, ALEQ-R), cognitive vulnerability (CTI-C, CRSQ, ACSQ), interpersonal vulnerability (CDEQ), personality (NEO-FFI-3), and EMA PANAS Forecasting. Adolescents will also complete the same fMRI task and the PRT task as completed at the pretreatment/baseline assessment.

Parents will complete the same self-report (BDI-II, SHAPS, TEPS, PANAS, PSS) and parent-report measures (MFQ-PR, MASC-PR) as they completed at the initial assessment.

Debriefing for Active Treatment Cohort and Their Parents:

Within one week of concluding post-treatment study session, the treatment group subject and parents will be debriefed. Specifically, the subject and parents will receive a summary including: (a) pre- and post-treatment diagnosis, (b) pre- and post-treatment changes in depressive and anxious symptoms, (c) recommendations for treatment moving forward (if necessary), and (d) a list of clinical resources in the greater Boston community if family is interested and/or would benefit from continuing treatment.

Debriefing for All Subjects

Following the final assessment, all subjects will be debriefed regarding the two monetary reward tasks (i.e., fMRI reward task and the PRT). Specifically, (s)he will outline the purpose of the study and explain the purposes of the scans and tasks. The study staff member will explain the differential reinforcement schedule utilized in the PRT. They will explain the partial contingency between the accuracy of the subject's choices and his/her likelihood of receiving positive feedback, and the rationale for use of this paradigm. Similarly, study staff will explain the our interest in probing reward-circuitry function during reward anticipation and outcome (i.e., wins, losses, neutral outcomes) for the fMRI task.

G. Follow-up Assessments

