The anhedonic participants completing the BA treatment and the healthy control participants will complete follow-up assessments at 3-, 6- and 12- months post-treatment, and these assessments will be conducted using REDCap, a secure, Partners-approved tool for collecting participant data. During the 3- and 6-month follow-up assessments, the adolescents will be asked to complete self-report symptom measures (CES-D, MFQ, SHAPS, TEPS, PANAS, MASC, PSS, ALEQ-R), which will necessitate approximately 20 minutes. The participating parent will be asked to complete self-report measures (BDI-II, SHAPS, TEPS, PANAS, PSS) and a parent-report measure of their child's symptoms (MFQ-PR, MASC-PR). At the 12-month follow-up assessment, adolescents

PARTNERS HUMAN RESEARCH COMMITTEE DETAILED PROTOCOL

and their parents will complete the above measures, and adolescents will also complete additional measures examining cognitive and interpersonal vulnerability (CTI-C, CDEQ, CRSQ, ACSQ) necessitating approximately 25 minutes. In addition, in order to assess for any changes in diagnoses during the follow-up phase, the K-SADS (including full depression module) will be completed over the phone with anhedonic participants at the 6- and 12-month assessments. Just the depression and anxiety disorder modules of the K-SADS will be completed over the phone with healthy participants at the 6- and 12-month assessments. Study staff will schedule these assessments at a time when both the parent and participating teen will be at home, and staff will speak to the parent before and after speaking with the adolescent.

After completing the 12-month follow-up, participants will be added to an email list to receive a quarterly lab newsletter, which will communicate results from our research to participating families. Past participants may opt out of receiving this newsletter at any time.

VI. BIOSTATISTICAL ANALYSIS

Data from this study will consist of demographic information, semi-structured clinical interviews (K-SADS, MINI), adolescent self-report symptom measures (MFQ, CES-D, SHAPS, TEPS, MASC, PANAS), parent self-report measures (BDI-II, SHAPS, TEPS, PANAS, PSS), cognitive vulnerability measures (CRSQ, ACSQ, CTI-C), an interpersonal vulnerability measure (CDEQ), stress measures (ALEQ-R, PSS), a personality measure (NEO-FFI-3), EMA data, behavioral data (PRT), and MR/fMRI data.

Sample Size

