For EMA, the primary variables of interest will be scores on the positive/negative affect and anhedonia items over the assessment periods. In addition, passive accelerometer data from the Beiwe app will provide data on amount of movement per day, which will be used to predict changes in self-reported affect and depressive symptoms. Given the longitudinal (i.e., repeated waves of EMA data) and hierarchical (i.e., assessment timepoints nested within individuals) structure of the data to be collected, Growth Curve Modeling (GCM) will be used to analyse EMA data (see *Statistics* below).

fMRI Processing:

fMRI: Gradient echo T2*-weighted echoplanar images will be acquired using the University of Minnesota multi-band BOLD EPI sequence (Feinberg et al., 2010; Moeller et al., 2010; Xu et al., 2013), which achieves excellent temporal and spatial resolution (TR/TE: 1300/35ms; FOV: 224 mm; matrix: 64X64; 78 slices; in-plane resolution: 2mm; voxels 2 x 2 x 2mm, multiband factor of 6). The EPI acquisition will use prospective motion correction to minimize the effects of subject motion. Analyses will be conducted using SPM8 and FreeSurfer (Fischl et al., 2002). Pre-processing will include motion/slice-time correction, removal of slow linear trends, intensity normalization, and spatial smoothing (6-mm).

Statistics:

GCM will be used to test the hypothesis that pretreatment reward dysfunction (fMRI, PRT, EMA), controlling for overall pretreatment levels of depressive symptoms (BDI), will predict anhedonic (SHAPS) symptom improvement over the course of BA. Given our multimodal assessment of reward system dysfunction, pretreatment predictors will include: (1) self-reported anhedonia (i.e., baseline EMA), 2) neural (i.e., striatal and mPFC) response to monetary rewards on the fMRI reward task and (3) reward learning scores on the PRT. The dependent variable in these analyses will be anhedonic (SHAPS) symptom improvement. GCM is well-suited for handling repeated symptom assessments over time (i.e., session-to-session SHAPS scores), as well as accommodating missing observations in longitudinal datasets.

With regards to fMRI analyses, data will be analyzed using an ROI approach to evaluate *a priori* hypotheses, followed by a whole-brain analysis to test regional specificity of findings. In the first approach, regression coefficients (“beta weights”) will be extracted

PARTNERS HUMAN RESEARCH COMMITTEE DETAILED PROTOCOL

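### The Aim 2(a) growth model adjusts for a BDI score that adolescents never complete, and the plan does not say which adolescent depression measure is meant

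*Combined protocol and SAP*

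**What the plan says.** Section VI (Statistics) describes the Aim 2(a) model: pretreatment reward dysfunction from fMRI, PRT and EMA, "controlling for overall pretreatment levels of depressive symptoms (BDI), will predict anhedonic (SHAPS) symptom improvement over the course of BA". The same hypothesis in Section II names no instrument: "controlling for overall pre-treatment levels of depressive symptoms, will predict anhedonic".

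The BDI-II is described once, in the parent's initial assessment (Section V.A): "The BDI-II is a 21-question self-report inventory for measuring the severity of depression". It recurs on the MRI day (Section V.D): "The Parent will complete the BDI-II, SHAPS, PANAS and MFQ-PR". It recurs again after treatment (Section V.F): "Parents will complete the same self-report (BDI-II, SHAPS, TEPS, PANAS, PSS". It is also in the parent battery at follow-up (Section V.G).

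The data inventory that opens Section VI keeps the two respondents apart. For adolescents it lists "adolescent self-report symptom measures (MFQ, CES-D, SHAPS, TEPS, MASC, PANAS"; for parents it lists "parent self-report measures (BDI-II, SHAPS, TEPS, PANAS, PSS". The adolescent post-treatment battery in Section V.F has "self-report measures assessing symptoms/affect (MFQ, CES-D, SHAPS, TEPS, MASC, PANAS" and no BDI. Table 1, the schedule for the treated adolescents, has no BDI row.

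**The concern.** Aim 2(a) claims that reward dysfunction predicts SHAPS improvement over and above the adolescent's general level of depression. The depression covariate is what gives the claim that meaning, and the Sample Size part of Section VI places prediction of symptom improvement within the primary aim.

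The covariate named there does not exist for the people being modelled. Someone running the analysis must substitute something, and the plan does not say what. If the choice is made with the data in hand, whether a reward predictor reaches significance can depend on it, and a reader of the results could not tell.

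**Working it through.** **Step 1. Is there an adolescent BDI?** I checked every place where a battery is listed.

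| Place | Adolescent depression measures | BDI-II |
|---|---|---|
| V.A and V.B, Day 1 | CDRS-R, CES-D, MFQ | parent only |
| V.C and V.D, Day 2 | CES-D, MFQ | parent only |
| V.E and Table 1 | CES-D, MFQ, CDRS-R | none |
| V.F, post-treatment text | MFQ, CES-D | parent only |
| V.G, follow-up | CES-D, MFQ | parent only |
| VI, data inventory | MFQ, CES-D | parent only |

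Adolescent BDI assessments scheduled: 0.

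**Step 2. How many scores could replace it?** Table 1 has two columns labelled pre-treatment, Pre I and Pre II.

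- CES-D: Pre I and Pre II (2)
- MFQ: Pre I and Pre II (2)
- CDRS-R: Pre I only (1)

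Total: 2 + 2 + 1 = 5. If only the two self-reports at one visit are considered, the choice is between 2.

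**Step 3. What could the choice do?** The plan gives no figure to reproduce, and no correlations, reliabilities or alpha, so what follows is illustration only. Let D be true depression severity, X a reward predictor and Y the person's SHAPS slope, all with unit variance:

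- X = cD + error and Y = cD + error, with no direct effect of X on Y
- score j: M_j = rD + error, with r = 0.8 or 0.9
- errors of the scores correlate 0.8 within an instrument and 0.5 between instruments
- n = 35 (Sample Size part of Section VI); least squares of Y on X and one score; two-sided 5% test of X (assumed); 40,000 simulated data sets per setting

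False-positive rates, given as r = 0.8; r = 0.9:

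| c | One fixed score | Best of five | Excess, points |
|---|---|---|---|
| 0.2 | 0.051; 0.050 | 0.070; 0.064 | 1.3 to 1.8 |
| 0.3 | 0.052; 0.051 | 0.076; 0.069 | 1.8 to 2.3 |
| 0.5 | 0.091; 0.061 | 0.140; 0.093 | 3.2 to 4.9 |

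The excess comes from unrounded rates, so it can differ by 0.1 from the difference of the rounded columns. If the choice is only between MFQ and CES-D at one visit, the excess falls to about 0.7 to 1.2 points at c = 0.2 to 0.3, and about 1.6 to 2.3 at c = 0.5.

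**Step 4. What belongs to the label and what does not.** Even one fixed score gives more than 5% at c = 0.5. The partial correlation of X and Y given M is c²(1 − r²)/(1 − r²c²). For c = 0.5 and r = 0.8 this is 0.25 × 0.36/(1 − 0.64 × 0.25) = 0.09/0.84 = 0.107, not zero. That part is measurement error in the covariate. Only the excess column concerns the unnamed instrument.

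**Limits.** The simulation has one predictor and no missing sessions. The plan lists EMA, several regional fMRI and PRT predictors, so these percentages do not carry over to the planned model.

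**The case against.** The strongest reply is that this is a one-word slip. The construct and timing are clear from Sections II and VI: overall depressive symptoms of the treated adolescents before treatment. A reader might infer that the sponsor plans to adjust for parental depression. The documents do not support that as an intention; it is only what the label literally says. The slip reading is probably right, but a slip is harmless only when one correction is evident. Here three instruments and two visits fit, and no section names a main depression measure.

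A reader might also count more than five candidates, by adding the MFQ and CES-D taken at session 1 or the parent-rated MFQ-PR. Neither holds up well. Table 1 puts session 1 under treatment sessions and reserves the pre-treatment label for Pre I and Pre II. MFQ-PR is a parent's rating, is not in Table 1, and is an unlikely reading of a self-report label.

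It is fair to add that the Section VI data inventory omits CDRS-R, which makes MFQ and CES-D the closest like-for-like substitutes. That narrows the likely choice but does not settle it, since the inventory may be incomplete and the visit stays open.

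Finally, the sizes rest wholly on assumed correlations and are modest. That stands. The point depends on the undefined covariate, not on the simulation.

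**Conclusion.** The covariate rule is wrong as written: it names an instrument that adolescents do not complete, and the intended replacement cannot be recovered from the documents. That much is certain from the text.

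The size is not. On the stated assumptions at n = 35, selecting the most favourable score adds roughly 1 to 2 percentage points at c = 0.2 to 0.3 and about 1.5 to 5 at c = 0.5. The lower ends correspond to two scores in play and the upper ends to five. A reader might take the 14% in the table as the cost of the label, but at r = 0.8 about 9% is present with any single fixed score.

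Nor do the documents support extending the point to the other analyses: only the Aim 2(a) model uses this covariate. It is a small should-fix.

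**What to change.** Before analysis, replace the BDI label in Section VI (Statistics) with one adolescent depression measure already in Table 1, at one stated pre-treatment visit, and use the same wording in Aim 2(a) of Section II. Suitable examples are:

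- MFQ or CES-D at Pre II, which are in the Section VI inventory and coincide with the fMRI and PRT
- CDRS-R at Pre I, the clinician-rated measure

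Any one of these closes the gap if fixed in advance. Report the remaining measures, each at a stated visit, as sensitivity analyses.

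The cost is wording and a few extra model fits. No new data, visits or participants are needed. The change does not remove the residual confounding from measurement error shown in Step 4, so that should be acknowledged when the result is interpreted.
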